9.4 Analysis of Vital Signs

Descriptive statistics for vital signs (systolic and diastolic blood pressure, pulse rate, weight, respiration rate, and temperature) and their changes from baseline at each assessment timepoint will be presented by study intervention group.

Selected vital signs will be considered potentially clinically significant (PCS) if they meet either the lower-limit or upper-limit PCS criteria listed in Appendix C. The number and percentage of participants who have PCS postbaseline vital sign values will be tabulated by study intervention for each postbaseline visit assessments. The percentages will be calculated relative to the number of participants who have available baseline values for those parameters with the change from baseline value criterion or non-PCS baseline values for those vital sign parameters without the change from baseline value criterion and at least 1 postbaseline assessment. The numerator will be the total number of participants with at least 1 PCS postbaseline value.

9.5 Analysis of Electrocardiograms

Descriptive statistics for ECG parameters (heart rate, PR interval, QRS duration, QT interval, and QTc) at baseline, Exit visit (pre-CAE and post-CAE) or Early Termination visit, and changes from baseline at the Exit visit will be presented by study intervention group.

ECG values will be considered potentially clinically significant (PCS) if they meet either the lower-limit or upper-limit PCS criteria listed in Appendix C. The number and percentage of participants who have PCS postbaseline ECG values will be tabulated by study intervention for Exit visit (pre-CAE and post-CAE) and Early Termination visit assessments. The percentages will be calculated relative to the number of participants who have available non-PCS baseline values and at least 1 postbaseline assessment. The numerator will be the total number of participants with at least 1 PCS postbaseline value.

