8.1.7. Electrocardiograms

The ECGs will be conducted for all participants in Stage 1 and for approximately 20% of participants (no fewer than 10 participants per study intervention arm) in Stage 2. During Stage 2, ECGs will only be conducted at selected sites. A standard 12-lead ECG will be performed in the supine position at the nominal times (relative to dosing) as outlined in the SoAs (Section 1.3). Assessments performed outside this window will be noted as protocol deviations, and the reason for deviation must be documented in the source documents. In Stage 1, predose ECGs at Visit 5 must be performed within 120 minutes prior to dosing. In Stage 2, predose ECGs at Visit 6 must be performed within 240 minutes prior to dosing. The ECG equipment will be provided to the sites by a central reading center for use during this study. Sites will receive training on the use of ECG equipment. Sites will transmit ECG data to the central reader after interpretation of the results is performed by a qualified physician or designee at the site.

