9.4.2.4. Electrocardiograms

For each stage, descriptive statistics for ECG parameters (heart rate, PR interval, QRS duration, QT interval, and QTc) at baseline, Exit visit or Early Termination visit, and changes from baseline at the Exit visit will be presented by study intervention.

The criteria for PCS ECG values will be detailed in the SAP. The number and percentage of participants who have PCS postbaseline ECG values will be tabulated by study intervention for Exit visit or Early Termination visit assessments. The percentages will be calculated relative to the number of participants who have available non-PCS baseline values and at least 1 postbaseline assessment. The numerator will be the total number of participants with at least 1 PCS postbaseline value.

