2.4 Sample Size Determination

For Stages 1 and 2, the sample size is not based on statistical considerations and is determined empirically. Approximately 322 participants (72 in Stage 1 and 250 in Stage 2) will be enrolled in the study. No participant can be enrolled in more than 1 cohort and/or stage of the study.

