3.0 Endpoints

3.1 Safety Endpoints

Safety endpoints are listed as the following:

AGN-242428 and AGN-231868 2012-201-005 – Statistical Analysis Plan (Stage 2) Version 1.0 – 07 December 2021

- adverse events (AEs),
- clinical laboratory values at the Exit/Early Termination visit,
- vital signs at each post-baseline visit,
- electrocardiogram (ECG) findings at the Exit/Early Termination visit,
- intraocular pressure (IOP) at each post-baseline visit,
- best-corrected visual acuity (BCVA) at each post-baseline visit,
- slit-lamp biomicroscopy findings at each post-baseline visit,
- dilated fundus (ophthalmoscopy) examination findings at the Exit/Early Termination visit.
- Drop Tolerability Questionnaire score at each post-baseline visit.

For eye-related endpoints, both eyes will be included in the analysis.

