5.6.3.4. Electrocardiogram

Descriptive statistics for ECG parameters (heart rate, RR interval, PR interval, QRS interval, QT interval, and QTc) at Baseline and Exit/Early Termination visits, and changes from baseline values at Exit/Early Termination visit will be presented by cohort and study intervention group.

The QTc will be calculated using the Fridericia correction (if the vendor does not provide). QTcF are derived as follows:

^b Visit will be used as baseline for change from baseline summaries.

^c Exit: Final or early termination visit.

Safety Statistical Analysis Plan

2012-201-005 [Stage 1]

Table 5-10 Derivations of OTcF

Parameter	Derivation if RR available	Derivation if RR unavailable
QTcF	QT	QT
(QTc Fridericia)	cubic root of RR	cubic root of 60/HR

ECG parameter values will be considered PCS if they meet either the lower-limit or higher-limit PCS criteria listed in Table 6-7. The number and percentage of participants who have at least one PCS post-baseline ECG values will be tabulated for all participants by cohort and study intervention group. The percentages will be calculated based on the denominator of the number of participants with available non-PCS baseline values and at least one post-baseline value and the numerator of the number of participants with non-PCS baseline value and at least one PCS post-baseline value.

A supportive listing of participants with postbaseline PCS values will be provided, including the participant number and baseline and postbaseline values, for the safety population.

Table 5-11 ECG Summaries

Endpoint	Description	Timing	Methodology
PCS values	Summary by parameter and PCS criteria Participants with baseline PCS values excluded from analysis Parameters and PCS criteria specified in Sections 6.5.4.2 and 6.5.4.3, respectively.	Screening ^b , Exit ^c	PCS descriptives/ Supportive data Listing ^a
Descriptives	Summary by parameter and analysis visit Parameters specified in Section 6.5.4.3	Screening ^b , Exit ^c	CFB descriptives

^a Participants who report ≥ 1 postbaseline PCS value and all ECG will be listed.

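### Stage 2 ECG change from baseline is summarised only at Exit, so Early Termination ECGs are left out although the endpoint includes them

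*SAP*

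**What the plan says.** - **Endpoint.** Stage 2 SAP 3.1 lists "electrocardiogram (ECG) findings at the Exit/Early Termination visit".
- **Stage 2 analysis.** Stage 2 SAP 9.5 gives observed ECG values at baseline and at Exit (pre-CAE and post-CAE) "or Early Termination visit, and changes from baseline at the Exit visit will be presented by study intervention group". The next paragraph tabulates PCS counts for Exit and for Early Termination.
- **Protocol.** Section 9.4.2.4 has the same structure: "Exit visit or Early Termination visit, and changes from baseline at the Exit visit will be presented by study intervention".
- **Meaning of Exit in Stage 2.** Stage 2 SAP 5.0 ties Exit to the Day 42 visit and counts anyone who leaves sooner as discontinued. Protocol Table 1-2 gives Early Termination its own column, with an ECG marked in it.
- **Stage 1.** Stage 1 SAP 5.6.3.4 says that "changes from baseline values at Exit/Early Termination visit will be presented by cohort and study intervention group". The footnote to its Table 5-11 defines Exit as the final or early termination visit.
- **Size of the ECG subset.** Protocol 8.1.7 plans ECGs for "approximately 20% of participants (no fewer than 10 participants per study intervention arm) in Stage 2".

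**The concern.** One sentence of Section 9.5 names Early Termination for values and leaves it out for change. Because Exit means Day 42 in Stage 2, the omission has an effect. A participant with a baseline ECG and an Early Termination ECG has a computable change, but the change summary has no place for it.

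ECG is the only safety measure treated this way in the Stage 2 SAP. Laboratory and vital-sign changes are given at each assessment time point (9.3, 9.4), and BCVA and IOP changes at each post-baseline visit (9.6, 9.7). Protocol 9.4.2.2 gives laboratory change at Exit or Early Termination. No reason is offered for handling ECG differently.

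ECG findings belong to the Stage 2 primary safety objective, and AGN-231868 had no human exposure by any route before this study (Protocol 2.2.2.4). As written, the mean and median change describe completers only. Those left out are people who stopped early, some of them for adverse events, and the protocol synopsis says that participants withdrawn for adverse events are not replaced.

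**Working it through.** **1. The plan's own figure.** The inputs are 250 Stage 2 participants (SAP 2.4: "Approximately 322 participants (72 in Stage 1 and 250 in Stage 2) will be enrolled in the study"), five arms allocated equally (SAP 2.3), and ECGs in about 20% (Protocol 8.1.7).

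- ECG participants: 0.20 × 250 = 50
- Per arm: 50 / 5 = 10

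This agrees with the stated minimum of 10 per arm.

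**2. What the text includes at each visit in Stage 2.**

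| ECG display (Stage 2 SAP 9.5) | Exit, Day 42 | Early Termination |
|---|---|---|
| Observed values | yes | yes |
| PCS counts | yes | yes |
| Change from baseline | yes | not named |

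**3. Chance that an arm of 10 is affected.** The documents state no early-termination rate, so p is assumed. If every early leaver attends the Early Termination visit, P(at least one change value lost) = 1 − (1 − p)^10.

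| Assumed p | Expected loss per arm (10p) | P(at least one lost) |
|---|---|---|
| 5% | 0.5 | 1 − 0.95^10 = 0.40 |
| 10% | 1.0 | 1 − 0.90^10 = 0.65 |
| 15% | 1.5 | 1 − 0.85^10 = 0.80 |

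These are upper bounds for an arm of 10. If only a fraction a of leavers attend, the chance is 1 − (1 − ap)^10. For example, with p = 10% and half attending, it is 1 − 0.95^10 = 0.40 instead of 0.65.

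**4. What a lost value costs in precision.** The 95% confidence half-width for a mean change, in SD units, is t(0.975, n − 1)/√n.

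| n | Half-width (SD) |
|---|---|
| 10 | 0.715 |
| 9 | 0.769 |
| 8 | 0.836 |
| 7 | 0.925 |

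Each lost value is 10% of an arm of 10. Precision is recovered only in a row that pools Exit with Early Termination; a separate Early Termination row leaves the Exit row at n = 9, 8 or 7.

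**5. What the PCS table still catches.** Stage 2 SAP Appendix C, Table 8, flags QTcF above 500 msec or an increase above 60 msec, and either is enough. QRS and PR have absolute thresholds only (150 and 250 msec). For early leavers with a non-PCS baseline, a large QTcF increase is therefore still counted. QTcF increases of 60 msec or less, and PR or QRS shifts that stay below the absolute limit, appear in no change display.

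**The case against.** The strongest reply is that little is hidden. Early Termination values are still summarised, large QTcF increases still enter the PCS count, and the Stage 2 safety analysis is descriptive (SAP Appendix E drops between-group tests). All of this stands, and it limits the size of the point.

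A second reply is that Section 3.1 speaks of findings and never mentions change, so 9.5 does not strictly contradict it. That is fair as far as it goes. But 9.5 does report change, and it reports it for fewer visits than the endpoint covers.

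A third reply is that Early Termination ECGs are not like-for-like. Exit ECGs are fixed at predose and at 45 ± 15 minutes postdose (Protocol Table 1-2). The Early Termination ECG falls on a variable day with no stated time relative to dosing. This is a good reason to keep the Exit rows unmixed and to footnote any pooled row. It is not a reason to report no Early Termination change, since the plan already summarises the values from those same recordings.

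A fourth reply is that some early leavers will have no ECG to recover. Protocol 7.1 only encourages the Early Termination visit after treatment is stopped, although 7.2 asks for every effort when a participant leaves the study. This stands too, and is why the probabilities are given as upper bounds. The table specifications are in a separate document, so the final layout cannot be checked here.

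**Conclusion.** The gap is real, small and easily closed. As written, Stage 2 SAP 9.5 leaves collected Early Termination ECGs out of the descriptive change summary. In an arm of 10, the chance of losing at least one such value is at most 40%, 65% or 80% at assumed early-termination rates of 5%, 10% or 15%. Those rates are assumptions, and the bounds suppose that every leaver attends the visit.

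Three stronger readings are tempting, and the documents do not support them:

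- *A QT signal in early leavers would go unseen.* The PCS table covers Early Termination and includes the 60 msec increase criterion. What is lost is the contribution of smaller changes to the mean and median.
- *The SAP departs from the protocol.* It follows Protocol 9.4.2.4. The mismatch is between the endpoint list and the analysis, and it looks like a drafting omission.
- *The Stage 1 SAP shows Early Termination change in its own row.* It pools Early Termination into Exit.

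**What to change.** Amend Stage 2 SAP 9.5 so that ECG change from baseline is presented at Exit (pre-CAE and post-CAE) and at Early Termination. Keep the Exit rows as they are.

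Add one last-on-study row that pools the Exit pre-CAE (predose) ECG with the Early Termination ECG, in line with the Stage 1 definition of Exit. This row is needed because a separate Early Termination row would usually hold only a participant or two per arm and would leave the Exit mean based on completers. Footnote the pooled row to say that Early Termination ECGs occur on variable days and have no fixed time relative to dosing.

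The cost is a few words in the SAP and two extra rows per ECG parameter. No new data are needed, because Table 1-2 already schedules the recording.

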9.6 Analysis of Best-corrected Visual Acuity

BCVA will be quantified using the Early Treatment Diabetic Retinopathy Study (ETDRS) visual acuity protocol. Descriptive statistics for BCVA and changes from baseline at each post-baseline visit will be presented by study intervention, and by study eye and nonstudy eye. Change from baseline will also be summarized by study intervention for each eye at each visit in a categorical tabulation as severe (\geq 30 letters decrease from baseline), moderate (\geq 15 and < 30 letters decrease from baseline) and no loss or mild (< 15 letters decrease from baseline).

9.7 Intraocular Pressure

Descriptive statistics for IOP and changes from baseline at each post-baseline visit will be presented by study intervention for each eye.

9.8 Biomicroscopy and Ophthalmoscopy

Biomicroscopy will be performed in each eye at each visit, by slit-lamp examination, without pupil dilation, including but not limited to lids/lashes, conjunctiva, cornea, and

anterior chamber. Observations for the examination will be graded on a 5-point scale (0=none, 0.5=trace, 1=mild, 2=moderate, 3=severe) except for a) the anterior chamber cells: 0=0 cells, +0.5=1-5 cells, +1=6-15 cells, +2=16-25 cells, +3=26-50 cells, and +4=> 50 cells; and b) flare: 0=none, +1=faint, +2=moderate, +3= marked and +4=intense).

will be summarized using descriptive statistics at all post-baseline visits and pre-/post-CAE when applicable. For Pre-CAE change from baseline, the Day 1 Pre-CAE value prior to the administration of the first administration of study intervention will be used as baseline. For Post-CAE change from baseline, the Day 1 Post-CAE value prior to the administration of the first administration of study intervention will be used as baseline.

The number of participants with biomicroscopy findings of ≥ 2-grade severity increase from baseline will be generated for MedDRA preferred terms recorded on the Ocular Biomicroscopic Exam eCRFs at each post-baseline visit by study intervention for each eye. For findings under other pathology which are not associated with a severity grade, a status change from absent to present will be treated as a 2-grade increase in the analysis. At least 2-grade increase in severity from baseline is defined as a change from no finding to 2 and above, from 0.5 to 2 and above, or from 1 to 3 and above from baseline at any of the follow-up visits. The number and percentage of participants with clinically significant biomicroscopy findings (at least 2-grade increase in severity from baseline) will be tabulated by finding category, and study intervention group.

The ophthalmoscopy findings will be summarized similarly.

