4.4. End of Study Definition

The end of the study is defined as the date of the last visit of the last participant in the study or last scheduled procedure shown in the SoA (Section 1.3) for the last participant in the study.

The Exit visit is defined as the last visit or the last scheduled procedure shown in the SoA for each stage of the study (Section 1.3). A participant is considered to have completed the study if he/she has completed all study visits including the Exit visit. If the participant is discontinued or withdraws from the study before the Exit visit, the last visit before the discontinuation or withdrawal will be considered an Early Termination visit.

5. Study Population

All participants will have DED. In addition, participants enrolled in Stage 2 of this study will have to respond to the CAE challenge with increased signs and symptoms of DED (see Sections 4.1 and 4.2.4 for more details).

Prospective approval of protocol deviations to recruitment and enrollment criteria, also known as protocol waivers or exemptions, is not permitted.

5.1. Stage 1

5.1.1. Inclusion Criteria for Stage 1

Participants are eligible to be included in Stage 1 of the study only if all of the following criteria apply:

1.	Age
1.01	Participant must be ≥ 18 years of age at the time of signing the informed consent
2.	Type of Participant and Disease Characteristics
2.01	Both of the following signs of DED in at least 1 eye at Screening and Baseline visits (the same eye does not need to qualify at both visits):
	 Total corneal fluorescein staining score ≥ 2 and ≤ 9 based on the NEI grading scale, with no score > 2 in any 1 region
	• Schirmer test with topical anesthesia score ≥ 1 and ≤ 10 mm/5 min
2.02	Symptoms of DED at both the Screening and Baseline visits as defined by an OSDI total score of ≥ 13 with ≤ 3 responses of "not applicable (NA)".
2.03	BCVA of 20/100 or better in both eyes at the Screening visit
2.04	Good general and ocular health, as determined by the investigator using medical history, ophthalmic examination and history, physical examination, fasting blood chemistry and hematology, urinalysis, vital signs, and 12-lead ECG results at the Screening and Baseline visits, as applicable per the SoA (Section 1.3).
3.	Sex
3.01	Male or female

4.	Contraceptives	
4.01	Male participants willing to minimize the risk of inducing pregnancy for the duration of the clinical study	

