9.3 Analysis of Laboratory Data

Descriptive statistics for values and changes from the baseline in standard units at each assessment time point will be presented by study intervention group.

Clinical laboratory test values will be considered potentially clinically significant (PCS) if they meet either the lower-limit or upper-limit PCS criteria listed in Appendix C. The number and percentage of participants who have PCS post-baseline clinical laboratory values will be tabulated by study intervention for all scheduled postbaseline visit. The percentages will be calculated relative to the number of participants who have available non-PCS baseline values and at least 1 postbaseline assessment. The numerator will be the total number of participants with at least 1 PCS postbaseline value.

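### The Stage 2 slit-lamp worsening count omits 2-to-4 rises in anterior chamber cells and flare, cannot show moderate-to-severe worsening, and has no stated percentage base

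*SAP*

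**What the plan says.** Slit-lamp biomicroscopy is one of the assessments for the primary safety and tolerability objective of Stage 2 (Protocol 3.2; Stage 2 SAP 2.1, Table 1). SAP 9.8 has most findings "graded on a 5-point scale (0=none, 0.5=trace, 1=mild, 2=moderate, 3=severe". Anterior chamber cells and flare go one grade further: "3=26-50 cells, and +4=> 50 cells" for cells and "3= marked and +4=intense" for flare.

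The section first plans a count, by visit and eye, of participants whose finding rises by two grades or more. It then plans a number and percentage of participants with such findings, which it labels clinically significant, "tabulated by finding category, and study intervention group". The rise is "defined as a change from no finding to 2 and above, from 0.5 to 2 and above, or from 1 to 3 and above". For ungraded other pathology, "a status change from absent to present will be treated as a 2-grade increase in the analysis". Ophthalmoscopy is to be summarized in the same way.

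Section 9.8 gives no denominator for the percentage. SAP 9.1 makes the safety population the general base. Other sections state their base. For laboratory values (9.3), "The percentages will be calculated relative to the number of participants who have available non-PCS baseline values", and 9.5 does the same for ECG. For vital signs (9.4), parameters judged partly on change from baseline use everyone with an available baseline value. The Stage 1 SAP (5.6.3.8) counts a slit-lamp increase of any severity.

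**The concern.** The list of qualifying changes stops at a baseline of grade 1. This raises three separate questions:

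- whether the list matches the two-grade threshold it is meant to define on every scale in the section;
- whether worsening from moderate to severe is visible in the table that carries the clinically significant label;
- what the percentage is a percentage of.

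The population gives the second and third questions some weight. Protocol Section 5 says that "participants enrolled in Stage 2 of this study will have to respond to the CAE challenge with increased signs and symptoms of DED", so some participants may enter with raised slit-lamp grades. SAP Appendix E removes all between-group safety tests, so the descriptive tables are the safety comparison. If moderate-to-severe worsening is absent from the headline slit-lamp table, a reader comparing drug with vehicle has to look for it elsewhere.

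**Working it through.** The plan states no rate, power or sample-size figure for this endpoint, so there is no figure to reproduce. The check has three steps.

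**Step 1. Every possible rise against the list.** Scales and list are from SAP 9.8.

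| Baseline | 0-3 scales (0, 0.5, 1, 2, 3) | Cells (0, 0.5, 1, 2, 3, 4) | Flare (0, 1, 2, 3, 4) |
|---|---|---|---|
| 0 | counted: 2, 3; not: 0.5, 1 | counted: 2, 3, 4; not: 0.5, 1 | counted: 2, 3, 4; not: 1 |
| 0.5 | counted: 2, 3; not: 1 | counted: 2, 3, 4; not: 1 | no such grade |
| 1 | counted: 3; not: 2 | counted: 3, 4; not: 2 | counted: 3, 4; not: 2 |
| 2 | counted: none; not: 3 | counted: none; not: 3, **4** | counted: none; not: 3, **4** |
| 3 | no rise exists | counted: none; not: 4 | counted: none; not: 4 |
| 4 | no such grade | no rise exists | no rise exists |

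- Cells and flare: 4 - 2 = 2, and grade 4 is also two steps above grade 2. The rise meets the threshold on either way of counting, yet it is not listed.
- 0-3 scales: 3 - 2 = 1. This is not a two-grade rise, so the list agrees with its threshold. The consequence is that a baseline of 2 or 3 leaves no countable outcome.
- An ungraded finding already present at baseline also has no countable outcome.

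**Step 2. Effect of the percentage base.** Let r be the event rate among participants able to meet the rule and p the share who cannot. Over the whole safety population the reported rate is

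R = r x (1 - p).

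Both r and p are assumptions. The planned arm size is 50 (Protocol 1.1), so 50 x (1 - p) participants are able to meet the rule.

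| p | Able to meet rule, of 50 | R if r = 10% | R if r = 20% |
|---|---|---|---|
| 0% | 50 | 10% | 20% |
| 10% | 45 | 9% | 18% |
| 20% | 40 | 8% | 16% |
| 40% | 30 | 6% | 12% |

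The shortfall is r x p, which is 1 to 8 percentage points for p from 10% to 40%, and nil at p = 0. With the same p in two arms, the ratio is r1(1 - p) / r0(1 - p) = r1/r0, unchanged, and the difference is (1 - p)(r1 - r0). For example, with assumed rates of 10% against 5% and p = 20%, the table shows 8% against 4%: the ratio is still 2, and the difference is 4 points instead of 5.

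**Step 3. Eyes and participants.** The percentage is per participant, and the SAP does not say how the two eyes combine. If either eye can qualify a participant, p counts only those with both eyes at grade 2 or above. Suppose 20% of eyes are at that level. Under independence between eyes, p = 0.20 x 0.20 = 4%, or 2 of 50. Under complete agreement, p = 20%, or 10 of 50. A share of eyes therefore cannot be read as a share of participants.

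**The case against.** The strongest defence is that the threshold is deliberate. Two grades is the planned cut-off, and Protocol 9.4.2.7 also uses it. A one-grade rise from 2 to 3 is left out just as 1 to 2 is. This stands: on the 0-3 scales the list misapplies nothing, and a row for 2 to 3 alone would single out one of several one-grade rises. The remaining point there concerns visibility.

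A reader might infer more: that eyes at grade 2 or 3 do stay in the base, and that worsening is therefore understated in this population. The documents do not support that as fact.

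- The base is unstated, and table specifications are in a separate document (SAP 1.0). The safety population is the likely default, but only by inference. A base of everyone with a baseline value would match the SAP's own vital-signs practice for change-based criteria.
- No baseline slit-lamp grades are given, and the Stage 2 sign thresholds are not in the public text. Responding to the challenge does not imply a moderate slit-lamp grade.
- Other outputs may show 2-to-3 changes. SAP 9.8 plans descriptive change-from-baseline summaries for an item whose name is missing from the public text. Ocular adverse events are tabulated by maximum severity. The adverse-event route is not certain, however: under Protocol Appendix 3, signs of the studied disease count only if more severe than expected, which is a matter of investigator judgement.

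The 2-to-4 gap needs 16 to 25 cells or moderate flare at baseline. Exclusion criterion 1.02 names inflammation not associated with dry eye as an example of a disqualifying condition, so such cases should be rare. The general two-grade wording also covers them. That limits the effect but does not remove the contradiction, because a programmer following the explicit list would score 2 to 4 as no event.

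**Conclusion.** The concern holds in a limited form.

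- **Definition.** For anterior chamber cells and flare the list contradicts the section's own two-grade rule by omitting 2 to 4. This needs no assumption, and its practical effect is probably small.
- **Visibility.** On the 0-3 scales, moderate-to-severe worsening cannot appear in the clinically significant table, whereas the Stage 1 rule would have counted it. This also follows from the text alone, but it concerns this one table and not all Stage 2 safety output.
- **Percentage base.** It is unspecified. If it is the whole safety population, the rate among participants able to meet the rule is understated by the factor (1 - p). The size is unknown because p is not in the documents. It is nil at p = 0, and the between-arm ratio is unaffected if p is equal across arms.

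The correction is worth making because the assessment serves the primary objective and the change is cheap. The documents do not establish that worsening will in fact be understated.

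**What to change.** In Stage 2 SAP 9.8:

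1. Add 2 to 4 for anterior chamber cells and flare to the listed changes.
2. Keep the two-grade table. For each graded finding, add either a count of any severity increase, as in Stage 1, or a shift table from baseline to worst post-baseline grade, so that 2-to-3 worsening can be seen alongside the other one-grade rises.
3. State the denominator, and show for each finding the number of participants whose baseline grade permits a two-grade rise: 1 or below on the 0-3 scales, 2 or below on the 0-4 scales. Say how the two eyes are combined in the per-participant percentage.

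No new data are needed. The cost is SAP text, extra table rows, and bases that differ by finding and must be displayed.
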